8.2 Classification of Adverse Events

8.2.1 Assigning Severity Rating for Adverse Events

8.2.1.1 Criteria for Determining Adverse Event Severity

The Investigator will make an assessment of the severity of each AE and SAE according to the National Cancer Institute CTCAE, v. 5.0, 2017. For terms not specified with the CTCAE, the criteria in Table 5 should be used to determine the grade severity.

Table 5: Criteria for Determining the Grade/Severity of Adverse Event Terms Not Specified by the National Cancer Institute CTCAE

Grade	Criteria
1	Mild; asymptomatic or mild symptoms, clinical or diagnostic observations only; intervention not indicated
2	Moderate; minimal, local, or noninvasive intervention indicated; limiting age-appropriate instrumental activities of daily living ^a
3	Severe or medically significant but not immediately life-threatening; hospitalization or prolongation of hospitalization indicated; disabling; limiting self-care activities of daily living ^b
4	Life threatening consequences; urgent intervention indicated
5	Death related to adverse event

a. Instrumental activities of daily living refer to preparing meals, shopping for groceries or clothes, using the telephone, managing money, etc.

b. Self-care activities of daily living refer to bathing, dressing and undressing, feeding self, using the toilet, taking medications, and not bedridden.

CTCAE = Common Terminology Criteria for Adverse Events.

AE severity should be recorded in the appropriate section of the AE CRF and in the subject's source documents.

8.2.1.2 Toxicity Management Criteria

8.2.1.2.1 Grade 1 or Grade 2 Adverse Event

Subjects who develop a Grade 1 or Grade 2 AE may continue investigational product at the discretion of the Investigator. Subjects who choose to withdraw from study due to a Grade 1 or 2 AE should have study withdrawal evaluations completed.

8.2.1.2.2 Grade 3 Adverse Event

Subjects who develop a Grade 3 AE should be managed as follows:

- If the Investigator has compelling evidence that the Grade 3 AE has not been caused by investigational product, then dosing may continue after discussion with the Medical Monitor.
- Subjects who develop a Grade 3 AE that the Investigator considers related to investigational product should have the investigational product discontinued. Subjects experiencing Grade 3 AEs requiring permanent discontinuation of investigational product should be followed weekly until resolution or stability of the AE and encouraged to have withdrawal study evaluations completed.

8.2.1.2.3 Grade 4 Adverse Event

Subjects who develop a Grade 4 AE should have investigational product permanently discontinued.

Subjects experiencing Grade 4 AEs requiring permanent discontinuation of investigational product should be followed weekly until resolution or stability of the AE and encouraged to have withdrawal study evaluations completed.

8.2.1.2.4 Folliculitis

Subjects using tapinarof topically may experience folliculitis. The majority if these events are mild and moderate and do not require intervention or interruption in study drug use. On close inspection, the morphology is similar to that of keratoses pilaris suggesting that the potential mechanism may be increased follicular cornification with subsequent follicular plugging. Importantly, AhR regulates the epidermal differentiation complex and tapinarof has been shown to repair the skin barrier through activation of stratum corneum components including fillagrin, hornerin and involucrin. This latter point suggests that the keratosis pilaris-like reaction may be an on-target effect associated with a therapeutic response to tapinarof cream.

While the majority of events have not required nor resulted in the need for intervention, several approaches can be employed to manage those patients with folliculitis who may be symptomatic including temporary interruption of study drug use at sites of folliculitis and/or the local application to affected areas of topical keratolytics such as 12% lactic acid lotion, 5-10% urea creams or lotions.

8.2.1.2.5 Other Management Criteria

The Medical Monitor should be notified if any of the following occur:

- Severe signs or symptoms, or significant changes in any of the safety assessments, that put the safety of the subject at risk (e.g., laboratory tests or vital signs, etc.) as judged by the Investigator.

8.2.2 Assigning Causal Relationship to Study Drug

The Principal Investigator or sub-Investigator is to make the causality assessment. The reasonable possibility of the relationship of an AE to study drug is to be assessed with careful medical consideration at the time of evaluation of an AE. The following definitions are to be used for the relationship of the adverse event to study drug:

- **Related:** A clinical event, including laboratory test abnormality, with a temporal relationship to study drug administration that makes a causal relationship plausible, unlikely attributed to concurrent disease or other drugs or chemicals, and that follows a clinically reasonable response

on re-administration (rechallenge) or withdrawal (dechallenge), although information on drug withdrawal may be lacking or unclear.

- **Not related:** A clinical event, including laboratory test abnormality, with a temporal relationship to study drug administration that makes a causal relationship improbable and/or in which other drugs, chemicals, or underlying disease provide a plausible explanation.

Any AEs /SAEs assessed as related to study participation (e.g., protocol-mandated procedures, invasive tests, or change in existing therapy) or related to study drug will be recorded from the time a subject consented to participate in the study up to and including any follow-up contact.

All AEs, whether related to study drug or not, must be fully and completely documented on the AE page of the CRF and in the subject's clinical record. In the event a subject is withdrawn from the study because of an AE, the primary reason for withdrawal (i.e., due to an AE) must be recorded on the CRF as such.

8.3 Time Period and Frequency for Event Assessment and Follow-Up

8.3.1 Adverse Event Reporting

All AEs will be collected from the time of signed informed consent until the final visit.

Any AEs assessed as related to study participation (e.g., protocol-mandated procedures, invasive tests, or change in existing therapy) will be collected from the time a subject consented to participate in the study up to and including any follow-up contact.

All SAEs will be recorded in the CRF and reported to the Sponsor within 24 hours via email or phone (refer to the [Medical Monitor / Sponsor Information Page](#) for contact information) (see Section [8.4](#)).

8.3.2 Follow-Up of Adverse Events

After the initial AE/SAE report, the Investigator is required to proactively follow each subject at subsequent visits/contacts. All SAEs and nonserious AEs will be followed until resolution, until the condition stabilizes, until the event is otherwise explained, or until the subject is lost to follow-up.

The Investigator will assess the outcome of each AE using the following criteria:

- **Recovered/Resolved:** The event has improved or subject recuperated.
- **Recovered/Resolved with sequelae:** The subject has recuperated but retained pathological conditions resulting from the prior disease or injury.
- **Recovering/Resolving:** The event is improving.
- **Not recovered/Not resolved:** The event has not improved or subject recuperated.
- **Unknown:** The outcome of the event is not known, not observed, not recorded, or refused.
- **Fatal:** Termination of life as an outcome of the AE.

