
 Incidence, frequency, and duration of treatment emergent adverse events (TEAEs) and serious adverse events (SAEs) Change from Baseline in laboratory values Change from baseline in vital signs Mean Investigator-assessed LTS scores by visit (overall and sensitive areas) Tapinarof plasma PK parameters on Day 1, if data permit, including: 
 area under the plasma concentration versus time curve from time zero to the last quantifiable concentration (AUC_{0-last}) maximum plasma concentration (C_{max}) time to maximum plasma concentration (t_{max}) time of last quantifiable concentration (t_{last}) Tapinarof plasma concentration on Day 28 	
Secondary:	

 Change in vIGA-AD™ score from Baseline at each study visit Proportion of subjects who have a vIGA-AD™ score of clear or almost clear (0 or 1) at each study visit Proportion of subjects with \geq50% improvement in EASI score from Baseline at each study visit Proportion of subjects with \geq75% improvement in EASI score from Baseline at each study visit Proportion of subjects with \geq90% improvement in EASI score from Baseline at each study visit Mean change and percent change in EASI score from Baseline at each study visit Mean change and percent change in %BSA affected from Baseline at each study visit Mean change and percent change in BSA x vIGA-AD™ values from Baseline at each study visit Proportion of subjects with a Baseline PP-NRS score \geq 4 who achieve \geq 4-point reduction in the PP NRS from Baseline at each study visit Proportion of subjects \geq 12 years old with a Baseline PP-NRS score \geq 4 who achieve a \geq 4-point reduction in PP-NRS score from Baseline at each study visit Proportion of subjects 2 to $<$ 12 years old with a Baseline PP-NRS score \geq 4 who achieve a \geq 4-point reduction in PP-NRS score from Baseline at each study visit Mean change in PP-NRS score from Baseline to Day 28 at each study visit by age group 	
Statistical Methods:	
Safety Analyses:	

 Analyses of the safety endpoints will be based upon the Safety population, which is defined as all enrolled subjects who receive at least 1 application of study drug. 	

- AEs will be summarized as incidence rates of any AEs, TEAEs, AEs of special interest, treatment-related TEAEs, TEAEs leading to study drug discontinuation, TEAEs leading to study discontinuation, and SAEs.

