8.1.3 Adverse Events of Special Interest

In prior clinical studies, contact dermatitis, folliculitis, and headache have been identified as AEs of particular clinical importance and will be reported as AESIs in this study.

In each case study drug may be continued or discontinued, based on Investigator judgment, and may be restarted when the event resolves. In addition, the following information should be collected for each of these AESIs:

Contact Dermatitis

The study site should collect location, time to onset, duration, size, associated symptoms (itching, burning, pain), severity (mild, moderate, severe), concomitant medications used to treat, action taken with study drug and photograph the affected site (if possible). If the subject contacts the study site to report significant skin irritation at or near the site of study drug application between study visits, the subject should be brought in for an unscheduled visit, if possible.

Headache

The study site should collect time to onset, duration, severity (mild, moderate, severe), location (e.g., frontal, temporal, occipital, diffuse).

Follicular Event

The study site should collect the location, duration, size, associated signs and symptoms (itching, burning, pain erythema), severity (mild, moderate, severe), describe morphology [scale (keratotic/cornified) or no scale (non-keratotic/non-cornified)], time to onset, and photograph the affected site (if possible). Additional information regarding management of folliculitis is provided in Section 8.2.1.2.4.

In particular, the term ‘folliculitis’ may not correctly describe the morphology of the observed local follicular events as these appear to be more consistent with a keratoses pilaris-like follicular based papule. Tapinarof upregulates components of the stratum corneum, including involucrin, hornerin, and filaggrin and increased cornification at, and subsequent mechanical occlusion of, the follicular ostia has been suggested to be a potentially on target mechanism by which these lesions may develop in some individuals treated with tapinarof cream. Additional morphologic description will help to more fully and appropriately characterize these follicular events.

Possible descriptors include, but are not limited to:

- Folliculitis
 - Non-inflammatory

- Inflammatory
- Milia
 - Non-inflammatory
 - Inflammatory
- Keratosis pilaris
 - Non-inflammatory
 - Inflammatory

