13.2 Adverse Events

All AE summaries will be restricted to treatment-emergent AEs (TEAEs), which are defined as those AEs that occurred after dosing and those pre-existing AEs (prior to first application of study drug) that worsened during the study. If it cannot be determined whether the AE is treatment-emergent due to a partial onset date, then it will be counted as such. The one exception will be the summary of Any AE which will include AEs not considered treatment-emergent. The summary of Any AEs will be reported in the Overall Summary of Adverse Events.

Verbatim terms in the eCRFs will be mapped to SOCs and PTs using MedDRA (Version 24.0).

For subjects not rolling over to the OL-LTE safety study, all reported AEs will be included in the open-label maximal use summaries. For subjects rolling over to the OL-LTE safety study, all

AEs with an onset date on or before the Week 4 visit date will be included in the open-label maximal use summaries.

Imputation of Start and End Dates of Adverse Event

To calculate duration of AEs, the following rules will be used where applicable to impute partial or completely missing start dates or end dates:

- If only the day is missing for a start date, the 1st of the month will be imputed. If the new estimated date falls before the date of first dose, while the known month and year match the month and year of the first dose, the date of first dose will be used as the new estimated date. The AE will be considered as a treatment-emergent AE (TEAE).
- If only the day is missing for an end date, the last day of the month will be imputed. If the new estimated date falls after the date of last study visit, the date of last study visit will be used as the new estimated date. Last study visit is defined as the Week 4 visit for those who elect to participate in the OL-LTE safety study, or the Week 5 Follow-up Visit for those who fail to qualify for participation in the OL-LTE safety study, or who qualify to participate but ultimately elect not to enroll.
- If both the day and the month are missing for a start date or end date, no imputation will be used, and the duration will not be calculated. However, if the year of start is the same or greater than the year of the first dose date, the AE will be considered as a TEAE.
- If the start date or end date is completely missing, duration will not be calculated. However, an event with completely missing start date will be considered as a TEAE.

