For treatment-emergent AESIs, summarization will be more extensive, reflecting the more detailed information collected. Information summarized will include number of events per subject, earliest onset day, duration (in days), causality, grade, and seriousness of AESIs, outcome, actions taken with study drug, assorted physical characteristics of the AESIs, and demographic/baseline characteristics and vIGA-AD™ status of the subjects experiencing them. Each type of AESI will be summarized separately. If a subject has more than one treatment-emergent occurrence of an AESI, the subject's maximum duration, highest levels of causality and seriousness, maximum grade and generally the most extreme level of each characteristic will be summarized. If an AESI was ongoing at end of study (EOS), it will not be included in the duration summary.

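### Improvement alone qualifies an adverse event as Recovered/Resolved and overlaps with Recovering/Resolving, so AESI outcomes, and possibly durations, cannot be read reliably

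*Protocol*

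**What the plan says.** Protocol 8.3.2 lists six outcome categories and makes them the criteria by which the investigator assesses each adverse event. Recovered/Resolved is "The event has improved or subject recuperated". Recovering/Resolving is "The event is improving". Not recovered/Not resolved is "The event has not improved or subject recuperated". The same section sets the length of follow-up: "All SAEs and nonserious AEs will be followed until resolution, until the condition stabilizes", with two further stopping points (the event is otherwise explained, or the subject is lost to follow-up). Resolution is not defined separately.

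The Protocol synopsis (Study Endpoints) places "Incidence, frequency, and duration of treatment emergent adverse events (TEAEs) and serious adverse events (SAEs" among the primary endpoints, and Section 2 does the same.

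SAP 13.2 works out duration from dates: "To calculate duration of AEs, the following rules will be used where applicable to impute partial or completely missing start dates or end dates". For TEAEs in general it lists incidence summaries only. For treatment-emergent AESIs (contact dermatitis, follicular events, headache) it goes further: "Information summarized will include number of events per subject, earliest onset day, duration (in days", together with outcome and other characteristics. An AESI ongoing at end of study is left out of the duration summary. SAP Appendix A counts a duration in days as the later date minus the earlier date, plus 1.

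**The concern.** An outcome scale works only if each event fits one category. Here an event that has improved but not cleared fits Recovered/Resolved, and while it goes on improving it fits Recovering/Resolving as well. About 12 sites will choose between the two categories with no rule to separate them.

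The first thing at stake is the AESI outcome table, which reports these codes directly in a study whose primary objective includes safety and tolerability. The second, under a further assumption, is duration. If a site closes an event as Resolved when it improves and enters that day as the end date, the recorded duration stops short of the real one. An AESI that should have been carried as ongoing would then be counted as finished.

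**Working it through.** The plan gives no figure on this point, so there is none to reproduce. The check sets the definitions side by side, follows outcome and end date into the SAP, and tests the direction of any effect on assumed dates.

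**Step 1. Where does an improved but still present event belong?** The categories come from Protocol 8.3.2; Unknown and Fatal do not bear on the question.

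| Category | Test set by the definition | Met by an improved, persisting event? |
|---|---|---|
| Recovered/Resolved | improved, or recuperated | Yes, on improvement alone |
| Recovered/Resolved with sequelae | recuperated, with lasting pathology | No |
| Recovering/Resolving | improving now | Yes, if still improving |
| Not recovered/Not resolved | no improvement | No |

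Two categories can apply at once, and none requires the event to be gone. The scale is also uneven: resolution with sequelae asks for recuperation, while the better outcome without sequelae does not.

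**Step 2. Effect on the outcome table.** This needs no assumption about dates, because outcome is summarised for each type of AESI. The planned numbers are about 36 subjects, with about 12 and at least 10 per age cohort (Protocol 4.1; SAP 5). Taking the cohort as denominator (an assumption; SAP 6 allows the total number of subjects for adverse event tables), one subject coded the other way moves a percentage by:

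- 1/36 = 2.8 points overall
- 1/12 = 8.3 points in a cohort of 12
- 1/10 = 10 points in a cohort of 10

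**Step 3. Effect on one event's duration.** Assumed dates: onset Day 5, improved Day 10, gone Day 20. By the SAP formula:

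- closed at improvement: 10 − 5 + 1 = 6 days
- closed when gone: 20 − 5 + 1 = 16 days
- difference: 16 − 6 = 10 days

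Closing at improvement can shorten a single event's recorded duration and never lengthens it. The size depends wholly on the assumed dates.

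**Step 4. Effect on the AESI duration summary.** Assume three subjects with finished AESIs of 3, 4 and 5 days and a fourth whose AESI is still present at end of study, one event each. Carried as ongoing, the fourth is excluded and the mean is (3 + 4 + 5)/3 = 4.0 days. Closed at improvement, it enters:

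| Days recorded for the fourth event | Mean |
|---|---|
| 2 | (12 + 2)/4 = 3.5 |
| 4 | (12 + 4)/4 = 4.0 |
| 10 | (12 + 10)/4 = 5.5 |
| 20 | (12 + 20)/4 = 8.0 |

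The summary can fall, stay the same or rise.

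**Step 5. Is the end date tied to the outcome code?** No. SAP 13.2 has rules for partial or missing end dates, and the formula uses dates without the outcome. Neither document says what date ends an event. Steps 3 and 4 are therefore conditional on site practice.

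**The case against.** The best defence is context. The label says Resolved, a separate category exists for events still on the way to recovery, and another covers lasting sequelae. Together these suggest that full resolution was meant, and many sites will read it so. This stands as evidence of intent. It does not remove the overlap, because 8.3.2 makes the written definitions the criteria to be used, and those definitions say something else.

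A second objection is that duration rests on dates, and that the annotated CRF and data management plan cited in SAP 2, which are not available here, may define the end date. This stands in full and is why the duration effect is stated as conditional.

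Third, the study is descriptive, with no hypothesis test, and the exposed summaries are confined to AESIs. This stands too and limits the weight of the point.

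Two stronger readings are tempting. A reader might infer that the wording also loosens the restart of study drug, since Protocol 8.1.3 says drug "may be restarted when the event resolves". That section uses the word in its ordinary sense, does not refer to the outcome codes, and leaves continuation to the investigator's judgement, so the documents do not show a link. A reader might also infer that follow-up ends too soon. Follow-up may already end once the condition stabilises, so the outcome definition is not the only thing that decides this.

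**Conclusion.** The overlap is certain from the text. It makes the AESI outcome summary unreliable: on the assumed denominators, one subject coded differently moves a cohort percentage by about 8 to 10 points.

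The duration effect is conditional on sites matching the end date to the outcome code. Under that assumption single events can be recorded too short, and AESIs still present at end of study can enter a summary meant to leave them out. The illustrated values (6 against 16 days; a mean of 4.0 becoming 3.5 to 8.0) show direction only and do not estimate size.

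A reader might infer that the definition shortens the primary endpoint and makes safety look better than it is. The documents do not support that. No passage sets the end date at first improvement, the AESI summary can move in either direction, and although duration of TEAEs and SAEs is named in the primary endpoint, the only duration summary the SAP lists is the one for AESIs. Nor do the documents say how long these events take to clear, so no typical gap between improvement and clearance can be claimed.

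**What to change.** In Protocol 8.3.2:

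- define Recovered/Resolved as the event no longer being present, or having returned to the subject's pre-event state;
- define Recovering/Resolving as improved but still present, with no end date entered;
- state that the adverse event end date is the date of resolution and not of first improvement.

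Use the same wording in the CRF instructions. The categories then no longer overlap for an improved event, and an AESI still present at end of study stays out of the duration summary, as SAP 13.2 intends.

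The cost is two definition lines and one end-date instruction, with no added visits or data. The downside is that some events will be reported as longer, or as ongoing.
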